2.2 Benefits and Risks to Subjects

Preclinical toxicology studies of ABBV-105 in animals and ex vivo human samples suggest that the potential risks to human subjects of ABBV-105 are anemia, bleeding associated with platelet

dysfunction, and lymphopenia. Reductions in lymphocytes and the known mechanism of action suggest the potential for an increased susceptibility to infection.

ABBV-105 alone and the ABBV-599 combination therapy (with upadacitinib) were well-tolerated with no serious adverse events (SAEs) observed in healthy adult subjects at various doses in 3 Phase 1 studies (Studies M16-356, M16-357, and M16-044). The current study is a continuation of the Phase 2 study of ABBV-105 and ABBV-599 in RA (Study M16-063). Taken together, the safety data from the Phase 1 program and the safe and successful completion of Study M16-063 support further development of ABBV-105 and ABBV-599 in Phase 2 in subjects with RA.

The data from over 4,000 RA patients treated with upadacitinib support an acceptable safety profile and a positive risk-benefit for treatment of adult patients with moderately to severely active RA.

Data from the primary efficacy analyses of the 5 pivotal Phase 3 clinical studies for the upadacitinib RA development program consistently demonstrated the efficacy of upadacitinib 15 mg QD and 30 mg QD, with both doses of upadacitinib meeting all primary and ranked key secondary endpoints across all studies which included all lines of therapy (methotrexate [MTX]-naïve, conventional synthetic disease-modifying antirheumatic drug [csDMARD]/MTX-inadequate responder [IR], and biologic disease-modifying antirheumatic drug [bDMARD]-IR). Upadacitinib 15 mg QD also demonstrated superiority over adalimumab across a broad range of efficacy measures. Overall, the efficacy data in the RA development program provide substantial evidence to support the use of upadacitinib as monotherapy or in combination with MTX and/or csDMARDs for the treatment of adults with moderately to severely active RA.

Serious infections and herpes zoster are identified risks for upadacitinib therapy. The rates of serious infections and herpes zoster for upadacitinib therapy are within the range of other marketed JAK inhibitor products.

In regarding to the potential for malignancy, per upadacitinib Investigator's Brochure version 18.0:

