5.8 Randomization/Drug Assignment

All subjects were assigned a unique identification number by the IRT at the screening visit for Study M16-063. Subjects who enter the study on active ABBV-105 and/or upadacitinib from Study M16-063 will continue on their previously-assigned treatment through the end of the LTE study. Subjects who previously received placebo treatment during Study M16-063 will receive ABBV-599 in the LTE study.

All AbbVie personnel with direct oversight of the conduct and management of the trial (with the exception of AbbVie Drug Supply Management Team), the investigator, study site personnel, and the subject will remain blinded to each subject's treatment throughout the study. To maintain the blind, the ABBV-105 capsules and matching placebo capsules and upadacitinib tablets and matching placebo tablets provided for the study will be identical in appearance.

In the event of a medical situation that requires unblinding of the study drug assignment, the Investigator is requested to contact the AbbVie Therapeutic Area Medical Director prior to breaking the blind. However, if an urgent therapeutic intervention is necessary which warrants breaking the blind prior to contacting the AbbVie Therapeutic Area Medical Director, the Investigator can directly access the IRT system via the Unblind Subject transaction, which is available to the Investigator. If the IRT system is unavailable, unblinding may occur by contacting EndPoint technical support via either phone (preferred) or email ([contact]). For country-specific phone numbers, please see the following website: <http://www.endpointclinical.com/help-desk/>. In the event that the blind is broken before notification to the AbbVie Therapeutic Area Medical Director, we request that the AbbVie Therapeutic Area Medical Director be notified within 24 hours of the blind being broken.

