### **4.0 Analysis Populations**

The following population sets will be used for the analyses.

The Full Analysis Set (FAS) includes all subjects who enrolled in Study M16-763 and received at least 1 dose of assigned study drug. The FAS will be used for efficacy and baseline analyses. Subjects will be grouped according to treatments as randomized for Study M16-063.

The Safety Analysis Set consists of all subjects who enrolled in Study M16-763 and received at least 1 dose of assigned study drug. Subjects will be grouped according to treatments actually received in Study M16-763. The Safety Analysis Set will be used for safety analyses.

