## **8.0 Efficacy Analyses**

### **8.1 General Considerations**

Analysis of efficacy endpoints will be conducted on the FAS.

For all efficacy endpoints, the descriptive statistics will be provided by treatment group. The statistics include number of observations, mean, standard deviation, minimum, median, and maximum for continuous variables; and number and percentage of subjects for categorical variables.

The analysis treatment groups will be described as follows indicating from Study M16-063 to extension Study M16-763:

- Group 1: ABBV-599 to ABBV-599

- Group 2: ABBV-105 60 to ABBV-105 60 mg
- Group 3: ABBV-105 20 to ABBV-105 20 mg
- Group 4: ABBV-105 5 to ABBV-105 5 mg, and
- Group 5: Upadacitinib to Upadacitinib
- Group 6: Placebo to ABBV-599
- Group 7: All ABBV-599 (Group 1 and 6)

"Baseline" refers to the last non-missing observation before the first administration of study drug in Study M16-063 or randomization in Study M16-063 if no study drug is given.

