### **9.2.1 Treatment-Emergent Adverse Events**

To summarize data from Study M16-763 only, a treatment-emergent Adverse Event (TEAE) is defined as an adverse event with an onset date that is on or after the first dose of study drug from Study M16-763, and no more than 30 days after the last dose of study drug from Study M16-763.

To summarize a combination of data from Studies M16-063 and M16-763, a treatment-emergent Adverse Event (TEAE) is defined as an adverse event with an onset date that is on or after the first dose of study drug from Study M16-063, and no more than 30 days after the last dose of study drug from Study M16-763.

Events where the onset date is the same as Study M16-063 study drug start date are assumed to be treatment-emergent. If an incomplete onset date was collected for an adverse event, the event will be assumed to be treatment-emergent unless there is other evidence that confirms that the event was not treatment-emergent (e.g., the event end date was prior to the study drug start date).

The number and percentage of subjects experiencing TEAEs will be summarized.

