### **9.3 Analysis of Laboratory Data**

Data collected from central and local laboratories, including additional laboratory testing due to an SAE, will be used in all analyses, except for Baseline, where SAE-related laboratory assessments on or before the first dose of study drug will be excluded.

Baseline is defined as the last available measurement before Study M16-063 study drug administration. The clinical laboratory tests defined in the protocol operations manual (e.g., hematology and clinical chemistry) will be summarized.

Mean change from baseline to each applicable post-baseline visit will be summarized for selected laboratory variables, with the number of observations, baseline mean, and visit mean, at each visit in Study M16-063 and Study M16-763 for each treatment group. An ANOVA model with only treatment as a factor, not controlling for baseline, will be used to test statistical significance for the mean change from baseline among different arms.

The baseline and post-baseline laboratory observations will be categorized as Grade 1, Grade 2, Grade 3, and Grade 4 according to OMERACT criteria (Rheumatology Common Toxicity Criteria v.2.0). For creatine phosphokinase and creatinine, NCI CTC criteria will be used.

For each laboratory variable, shift tables will be generated that cross tabulate the subjects as deemed appropriate by "as treated" treatment group:

- Category of the baseline value versus category of the final value.
- Category of the baseline value versus maximum category.
- Category of the baseline value versus minimum category.

Note that the minimum/maximum category is used, rather than the category of the minimum/maximum value. The two may be different due to variation in the reference range.

No statistical tests will be performed for this analysis.

Laboratory abnormalities will be evaluated based on Potentially Clinically Significant (PCS) criteria ([Appendix C](#)). For each laboratory PCS criterion, the number and percentage of subjects who have a laboratory value meeting the criteria will be summarized. Listings will be provided to summarize subject-level laboratory data for subjects meeting PCS criteria.

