#### **9.4 Analysis of Vital Signs**

Vital sign variables include sitting systolic blood pressure, sitting diastolic blood pressure, pulse, body temperature, and weight. The criteria for potentially clinically significant vital sign findings are presented in [Appendix C](#).

Mean changes from Baseline to post-baseline visits will be summarized with the baseline mean, the visit mean, change from baseline mean, standard deviation, and median. An ANOVA model with only treatment as a factor, not controlling for baseline, will be used to test statistical significance for the mean change from baseline.

The number and percentage of subjects meeting the criteria for potentially clinically significant vital sign values will be summarized.

Vital sign variables will be evaluated based on potentially clinically significant (PCS) criteria ([Appendix C](#)). For each vital sign PCS criterion, the number and percentage of subjects who have a vital sign value meeting the criteria will be summarized. Listings will be provided to summarize subject-level vital sign data for subjects meeting PCS criteria.

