**Laboratory Data**

**K. Haematology**

K1. Hgb (g/dl) decrease from pre-treatment	1.0 – 1.4	1.5 – 2.0	2.1 – 2.9, or Hgb < 8.0, > 7.0	≥ 3.0; or Hgb < 7.0
K2. Leukopenia (total WBC) × 1000	3.0 – 3.9	2.0 – 2.9	1.0 – 1.9	< 1.0

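### Group 6 (placebo to ABBV-599) has no laboratory baseline taken just before ABBV-599, so its baseline-relative results at extension visits mix placebo-period change with on-drug change

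*SAP*

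**What the plan says.** - **Laboratory baseline.** SAP 9.3 gives one rule for all groups: "Baseline is defined as the last available measurement before Study M16-063 study drug administration". Mean changes are tabulated by treatment group at the visits of both studies and compared across arms by ANOVA. Shift tables set the baseline category against the final, maximum and minimum category.
- **Switch.** Protocol 5.8: "Subjects who previously received placebo treatment during Study M16-063 will receive ABBV-599 in the LTE study". The activity schedule (Protocol Appendix D) places extension entry at Week 12.
- **Safety grouping.** SAP 4.0: "Subjects will be grouped according to treatments actually received in Study M16-763. The Safety Analysis Set will be used for safety analyses". SAP 6.0 labels the switchers Group 6, ABBV-599 After Placebo.
- **Baseline-relative grades.** SAP Table C-1 grades haemoglobin by "K1. Hgb (g/dl) decrease from pre-treatment". It does not define pre-treatment, and 9.3 holds the only laboratory baseline in the SAP. The footnoted creatinine grades include multiples of Baseline.
- **Vital signs.** SAP 9.4: "Mean changes from Baseline to post-baseline visits will be summarized with the baseline mean, the visit mean, change from baseline mean, standard deviation, and median". Neither 9.4 nor Table C-2 says which baseline is meant. The only other definition is in the efficacy section (SAP 8.1), where Baseline "refers to the last non-missing observation before the first administration of study drug in Study M16-063".
- **Adverse events.** SAP 9.2.1 defines a treatment-emergent event for M16-763-only summaries as "an adverse event with an onset date that is on or after the first dose of study drug from Study M16-763", within 30 days of the last dose. A second definition, for the combined studies, starts at the first M16-063 dose.

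**The concern.** For Groups 1 to 5, who stay on the same active drug, a value before M16-063 dosing is a proper pre-treatment value. For Group 6 it is a pre-placebo value, while the results are reported under ABBV-599. Anything that happened to a switcher's haemoglobin, creatinine or baseline category during 12 weeks of placebo is carried into the ABBV-599 result. The error can go either way: a fall on placebo appears as toxicity, and a rise on placebo masks a later fall on drug.

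Haemoglobin matters here because Protocol 2.2 says that "the potential risks to human subjects of ABBV-105 are anemia, bleeding associated with platelet" dysfunction, and lymphopenia. Haematology and chemistry mean changes, potentially clinically significant (PCS) values and liver elevations are also key safety outputs of the interim analysis (SAP 11.0), so the interim review would carry the same mixture.

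**Working it through.** **1. Gap between baseline and first ABBV-599 dose.** The last visit is Week 60 from M16-063 baseline and the extension treatment period is 48 weeks (SAP 2.3). 60 − 48 = 12 weeks, which matches the Week 12 entry column in Protocol Appendix D. The gap is nominal.

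**2. Share of the Group 6 change window spent on placebo,** 12 / visit week:

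| Visit | Weeks on ABBV-599 | Placebo share |
|---|---|---|
| Week 18 | 6 | 12/18 = 67% |
| Week 24 | 12 | 12/24 = 50% |
| Week 30 | 18 | 12/30 = 40% |
| Week 36 | 24 | 12/36 = 33% |
| Week 48 | 36 | 12/48 = 25% |
| Week 60 | 48 | 12/60 = 20% |

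With a baseline just before ABBV-599 the share is 0 at every visit.

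**3. Effect on individual results.** Table C-1 haemoglobin bands for a decrease in g/dl are 1.0-1.4 (Grade 1), 1.5-2.0 (Grade 2), 2.1-2.9 (Grade 3) and 3.0 or more (Grade 4). The subjects below are invented.

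| Change on placebo, then on ABBV-599 | From M16-063 baseline | From last value before ABBV-599 |
|---|---|---|
| Haemoglobin −1.2, then 0 | −1.2: Grade 1 | 0: none |
| Haemoglobin −1.0, then −0.5 | −1.5: Grade 2 | −0.5: none |
| Haemoglobin +0.8, then −1.6 | −0.8: none | −1.6: Grade 2 |
| Creatinine 0.7 to 0.9, then 0.9 (within ULN) | 0.9/0.7 = 1.29: Grade 1 | 0.9/0.9 = 1.00: none |
| Weight 70 to 74 kg, then 75.5 kg | 75.5/70 − 1 = +7.9%: meets >7% | 75.5/74 − 1 = +2.0%: does not |

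The weight row applies only if the vital-sign baseline is the pre-M16-063 one, which 9.4 leaves open.

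**4. What does not move.** White cells, neutrophils, lymphocytes, platelets, AST, ALT, bilirubin and CPK are graded on fixed or ULN limits, so the grade of a single value is the same under either baseline. The shift table's starting category can still change. Also, a value taken on placebo is later than the 9.3 baseline and so is post-baseline. The SAP does not say that such values are left out of Group 6's maximum or minimum category, or of the as-treated liver-test counts.

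**5. Illustration of size, on assumed inputs.** The documents give neither the SD of change nor any placebo drift. Assume a normal change, no ABBV-599 effect, and an SD of haemoglobin change of 0.7 g/dl (range 0.6 to 0.8). Then P(drop ≥ 1.0) = Φ((−1.0 − drift)/SD):

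- drift 0: Φ(−1.43) = 7.7% (4.8 to 10.6%)
- drift −0.3: Φ(−1.00) = 15.9% (12 to 19%)
- drift +0.3: Φ(−1.86) = 3.2% (1.5 to 5.2%)

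The drift-0 line is also what a pre-ABBV-599 baseline would give if the SD were unchanged. In the same way, for a systolic rise of at least 20 mmHg with SD 10 to 15 and placebo drift 3 to 5 mmHg, 4.5 to 15.9% would be flagged from the pre-M16-063 baseline, against 2.3 to 9.1% from Week 12.

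**The case against.** **Placebo-period change is visible.** SAP 9.3 tabulates mean change at visits in both studies, so a reader can see what happened before Week 12. This stands for group means, and it would be wrong to infer that the contrast is wholly lost. It does not repair subject-level grades, shifts or PCS counts. Subtracting the Week 12 mean from a later mean is also inexact, because data are not imputed and only 20 to 60% are expected to complete, so different subjects contribute.

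**Switchers are labelled separately.** SAP 6.0 keeps them apart from subjects always on ABBV-599, and the pooled ABBV-599 group appears only under efficacy. This stands: pooling in the laboratory tables is not established. A separate row still carries the mixed change.

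**A common baseline keeps the arms comparable.** This stands for the ANOVA. Re-basing Group 6 alone would compare a 48-week change with 60-week changes at Week 60. It is a reason to add a baseline for Group 6, not to replace the existing one everywhere.

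**Stronger readings that the documents do not support.**

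- Group 6 is not the only before/after ABBV-599 contrast. Group 1's M16-063 baseline also precedes ABBV-599.
- The anaemia adverse event of special interest is not distorted by the laboratory baseline. It is identified by a search of event terms (SAP Appendix B).
- The adverse-event and laboratory rules do not contradict each other. The combined-studies event window starts at the first M16-063 dose, as the laboratory rule does. What is missing is a laboratory counterpart to the M16-763-only window.
- SAP 9.4 does not fix a wrong vital-sign baseline. It fixes none.

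**Entry screening.** Entrants must not have met M16-063 laboratory discontinuation or toxicity criteria (Protocol 5.1). This may remove the largest placebo-period falls, and the normal model above ignores it.

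**Conclusion.** The point holds for Group 6. As written, its haemoglobin grades, the baseline-relative part of its creatinine grades, its shift-table starting categories and its mean changes at extension visits mix 12 nominal placebo weeks with time on ABBV-599. Placebo is two thirds of the window at Week 18 and one fifth at Week 60. No other section supplies a pre-ABBV-599 baseline. Two gaps go with it: placebo-period values are not excluded from Group 6 extreme-category and liver-test counts, and the vital-sign baseline is undefined.

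A reader might take the illustration to mean that haemoglobin toxicity in Group 6 will double or halve. That follows only from the assumed SD and a drift of 0.3 g/dl either way; the documents support neither figure, and the size of the bias cannot be computed from them. The mixing of periods does not depend on those assumptions. The plan should be changed, but the problem is confined to one group and to results measured against baseline.

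**What to change.** 1. In SAP 9.3, define an additional baseline for Group 6: the last value before the first M16-763 dose (the LTE Baseline/Week 12 assessment).
2. Use that baseline, and only values after that dose, for Group 6's ABBV-599 haemoglobin and creatinine grades, shift tables, PCS counts and liver-test counts. Add a Group 6 mean-change table from it.
3. In SAP 9.4 and Table C-2, state the vital-sign baseline, and apply the same Group 6 rule to the change-based blood pressure, pulse and weight criteria.
4. Keep the M16-063 baseline for Groups 1-5 and for the existing two-study mean-change table. Do not mix the two baselines in the across-arm ANOVA.

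No new data are needed: haematology, chemistry, vital signs and weight are already scheduled at Week 12 unless done as part of M16-063 (Protocol Appendix D). The cost is SAP wording, one derived flag and a second set of Group 6 rows, whose change window is shorter (at most 48 weeks, against 60).

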5.5 Withdrawal of Subjects and Discontinuation of Study

A subject may voluntarily withdraw or be withdrawn from the study at any time for reasons including, but not limited to, the following:

- Clinically significant abnormal laboratory results or AEs, which rule out continuation of the study drug, as determined by the investigator or the AbbVie Therapeutic Area Medical Director.
- Serious infections (e.g., sepsis) that cannot be adequately controlled within 2 weeks by anti-infective treatment or would put the subject at risk for continued participation in the trial as determined by the Investigator.

- The investigator believes it is in the best interest of the subject.
- The subject requests withdrawal from the study.
- Eligibility criteria violation was noted after the subject started study drug and continuation of the study drug would place the subject at risk.
- Introduction of prohibited medications or dosages and continuation of the study drug would place the subject at risk.
- Subject is non-compliant with tuberculosis (TB) prophylaxis (if applicable) or develops active TB at any time during the study.
- The subject becomes pregnant while on study drug.
- Malignancy, except for localized NMSC or carcinoma in-situ of the cervix.
- Subject is significantly noncompliant with study procedures, which would put the subject at risk for continued participation in the trial.
- Subject develops a gastrointestinal perforation.

In addition, the following discontinuation criteria also apply:

- Subjects not responding to therapy can discontinue study drug (or withdraw from study) at any time for any reason during the study in order to receive standard of care.
- Subjects who demonstrate worsening of joint count (SJC and/or TJC) at 2 consecutive visits (scheduled or unscheduled) should be discontinued from study drug and treated with standard of care at the discretion of the clinician.
- Starting at the Week 18 visit (after the Week 18 assessments have been performed) and at visits thereafter, subjects who fail to achieve at least 20% improvement in TJC and SJC should be discontinued.

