## **2.4 Sample Size Determination**

This is the LTE study for Study M16-063. All eligible subjects who completed Study M16-063 will be enrolled in this study if the subject signs and dates the informed consent. Based on discontinuation criteria mandating efficacy, it is estimated that 20 - 60% of subjects (i.e., between 40 and 120 subjects) will ultimately complete the LTE.

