## **9.0 Safety Analyses**

### **9.1 General Considerations**

Safety analyses will include reporting of adverse events, laboratory, and vital signs measurements. Safety analyses will be carried out using the Safety Analysis Set.

The following summary statistics will be presented for subjects who have both baseline and post-baseline values for laboratory parameters and vital signs: the mean value at Baseline and at each respective protocol specified visit, and the mean, standard deviation and median for changes from Baseline. Categorical data will be summarized using frequencies and percentages. The number of non-missing values will be given. Missing safety data will not be imputed.

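### The laboratory and vital-sign tests leave out a baseline value that every analysed subject has; adding it as a covariate is a free, modest gain in precision

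*SAP*

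**What the plan says.** SAP 9.3 (laboratory data) and SAP 9.4 (vital signs) give the same model: "An ANOVA model with only treatment as a factor, not controlling for baseline, will be used to test statistical significance". For laboratory data the test is "for the mean change from baseline among different arms".

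Four other passages set the context.

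- **Who is analysed.** SAP 9.1 presents these summaries for "subjects who have both baseline and post-baseline values for laboratory parameters and vital signs".
- **Which baseline.** SAP 9.3: "Baseline is defined as the last available measurement before Study M16-063 study drug administration". SAP 9.4 gives no separate definition for vital signs; the general definition in SAP 8.1 also points to the value before first dosing in M16-063.
- **Which visits and groups.** Laboratory results are shown with "baseline mean, and visit mean, at each visit in Study M16-063 and Study M16-763 for each treatment group". For the Safety Analysis Set, SAP 4.0 says: "Subjects will be grouped according to treatments actually received in Study M16-763".
- **How many subjects.** The only size figure is in SAP 2.4: "it is estimated that 20 - 60% of subjects (i.e., between 40 and 120 subjects) will ultimately complete the LTE".

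SAP 12.0 excludes hypothesis tests for efficacy and is silent on these safety tests. Protocol 7.4 plans summaries of mean change and names no test.

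**The concern.** Baseline is measured before any study drug, is already collected, and is present for everyone in the analysis. Leaving it out of the model discards information at no saving.

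Two consequences follow. First, subtracting baseline is the best adjustment only when a subject's later value moves one for one with baseline. At any lower correlation, part of the baseline noise stays in the change score and widens the interval for the arm difference. With a few tens of subjects per arm at most, that can matter for a moderate shift in a blood count, creatinine or blood pressure. Second, if the arms differ at baseline by chance, regression to the mean turns part of that difference into an apparent difference in change. Because one baseline serves every visit, the same artefact recurs at each visit and can look like a consistent effect over time.

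These two ANOVAs are also the only significance tests in the SAP, and they bear on the safety part of the objective.

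**Working it through.** **Inputs from the documents.** The model, the baseline definition and the restriction to subjects with a baseline come from SAP 9.1, 9.3 and 9.4. Expected completers are 40 to 120 (SAP 2.4). That figure is self-consistent: 40/0.20 = 120/0.60 = 200. The documents give no SD, alpha, power or correlation for these tests, so there is no stated figure to reproduce.

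**Assumptions.** Equal SD s at baseline and visit; correlation r from 0.3 to 0.9; two-sided 5%; five equal arms for the five treatments in SAP 2.3, so 40/5 = 8 to 120/5 = 24 completers per arm. Earlier visits would have more.

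**1. Precision.** Per-subject variance is 2s²(1 − r) for the change score and s²(1 − r²) with baseline as covariate. The ratio is (1 + r)/2, and the interval narrows by 1 − √((1 + r)/2).

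| r | Variance ratio | ANCOVA interval narrower by | Planned SE larger by |
|---|---|---|---|
| 0.3 | 0.65 | 19% | 24.0% |
| 0.5 | 0.75 | 13% | 15.5% |
| 0.7 | 0.85 | 8% | 8.5% |
| 0.8 | 0.90 | 5% | 5.4% |
| 0.9 | 0.95 | 3% | 2.6% |

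These are large-sample values. Estimating the slope multiplies the ANCOVA variance by about 1 + 1/(df − 2), where df is the within-arm degrees of freedom. With 8 per arm, df = 40 − 5 = 35 and the factor is 1 + 1/33 = 1.030. The narrowing is then 1 − √(0.75 × 1.030) = 12% at r = 0.5 and 1 − √(0.95 × 1.030) = 1% at r = 0.9. With 24 per arm, df = 115 and the factor is 1 + 1/113 = 1.009, which is negligible.

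**2. Power.** For a pairwise difference of 0.8 SD (illustrative), planned model to ANCOVA, using the large-sample variance ratio:

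| r | 8 per arm | 16 per arm | 24 per arm |
|---|---|---|---|
| 0.5 | 36% to 46% | 62% to 74% | 79% to 89% |
| 0.8 | 72% to 76% | 95% to 97% | 99.2% to 99.6% |

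**3. Chance imbalance.** A baseline difference d shifts the unadjusted difference in change by −(1 − r)d. The chance SD of d is s√(2/n): 0.50 SD at n = 8 and 0.29 SD at n = 24. A one-standard-error imbalance therefore contributes 0.25 and 0.14 SD at r = 0.5, and 0.10 and 0.06 SD at r = 0.8.

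**4. Type I error.** Averaged over possible imbalances, the planned test rejects a true null at the nominal rate: 4.3% to 5.7% in simulations of five arms of 8 or 24 (r = 0.5 or 0.8, 3,000 runs each). Given an imbalance of k standard errors, the test statistic has mean k√((1 − r)/2) in absolute value and SD √((1 + r)/2). At k = 1 the false-positive rate is about 5%. At k = 2 it is about 13% (r = 0.5) or 8% (r = 0.8).

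**5. Non-chance differences.** Simulated with a 0.5 SD baseline difference and no treatment effect:

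| Source of the difference | Planned ANOVA shift | ANCOVA shift |
|---|---|---|
| Selection on the measured baseline | −0.25 (r = 0.5), −0.10 (r = 0.8) | about 0 |
| Stable difference between groups | about 0 | +0.25 (r = 0.5), +0.10 (r = 0.8) |

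**The case against.** The strongest objection concerns selection. Only M16-063 completers can enter, and from Week 18 Protocol 5.5 says "subjects who fail to achieve at least 20% improvement in TJC and SJC should be discontinued". A reader might infer that the arms are therefore unbalanced and that ANCOVA would correct this. The documents do not support that inference. The visible selection is on completion, on meeting the feeder study's discontinuation criteria and on joint-count response, not on the baseline value of a given analyte. As step 5 shows, if groups differ stably over time the change score is right and ANCOVA is biased. Neither model repairs selection after randomisation. This objection stands against any claim that ANCOVA removes selection bias. It does not justify an unadjusted model alone, because keeping the unadjusted mean changes in view lets the reader compare the two.

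A second objection also stands: the harm is limited. Baseline means are tabulated, so an imbalance can be seen. Shift tables, counts of potentially clinically significant values, liver thresholds and confidence intervals for adverse events of special interest run alongside. Protocol 4.2 makes the primary comparison each arm against its own feeder-study profile, and no decision rule uses these p-values. It would go too far to say that the ANOVA could by itself hide a safety signal.

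Third, a reader might count the expected false positives over many analytes and visits. That is a multiplicity question that a covariate does not change. The number of variables tested is also not stated: SAP 9.3 refers only to a selection.

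**Conclusion.** The point holds as a matter of efficiency and of conditional bias. The planned model widens intervals for no benefit: an ANCOVA interval would be 19% to 3% narrower for r from 0.3 to 0.9, and slightly less than that with 8 per arm. It also passes a fraction (1 − r) of any chance baseline imbalance into the arm difference at every visit.

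Two stronger readings are not supported. The whole of an imbalance does not pass through, because baseline is already subtracted. The tests are not invalid either, because their overall error rate is nominal; only after a large chance imbalance does the false-positive rate rise to about 8% to 13%.

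The size rests on assumed r, equal variances and equal arms, none of which the documents give. If r is near 0.9 and arms are as small as 8, the gain is about 1%. The direction for chance imbalance is not in doubt at the sizes and correlations considered. Classification: free improvement, modest importance.

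**What to change.** In SAP 9.3 and 9.4:

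1. Replace the treatment-only model by an ANCOVA with treatment and the same parameter's M16-063 baseline value. State in 9.4 that vital signs use this baseline.
2. Report adjusted differences between arms with 95% confidence intervals, labelled descriptive. If any p-value is kept, give its status in SAP 12.0.
3. Keep the unadjusted mean changes already planned beside the adjusted differences.
4. Add a sentence that later-visit comparisons are between selected subsets of the randomised arms and that adjustment for baseline does not correct for this.

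The cost is one model term and a few sentences. No new data are needed, and no subject is lost, since all those analysed already have the covariate.
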